**Table 4. Schedule of Events**

Evaluation	Initial Screen	Rescreen (if applicable  )	Day 1  Base Line -2 hr pre-infusion	1 hr post infusion ± 15min	6 hr post -1 or +2 hr	Day 2 24 hr post ± 3 hr	If hospitalized			Day 6 (+ 4 days)	Day 30 (+2 days) (by phone)
							Day 3	Day 4	Day 5		
Visit #	1	1A	2	3	4	5	6	7	8	9	10
Sign ICF	X										
Verbal reconfirmation of informed consent		X	X	X	X	X	X	X	X	X	X
History and complete physical exam 	X										
WHO assessment	X	X	X	X	X	X				X	
Abbreviated physical exam 		X	X	X	X	X				X	
Pregnancy test (serum or urine)-applicable females only	X	X									
Concomitant medications (Medications, OTC Remedies, Herbal Preparations,	X	X	X	X	X	X	X	X	X	X	

Evaluation	Initial Screen	Rescreen (if applicable  )	Day 1  Base Line -2 hr pre-infusion	1 hr post infusion ± 15min	6 hr post -1 or +2 hr	Day 2 24 hr post ± 3 hr	If hospitalized			Day 6 (+ 4 days)	Day 30 (+2 days) (by phone)
							Day 3	Day 4	Day 5		
Vitamins, Supplements and IV fluids)											
Record transfused blood products 	X	X	X	X	X	X	X	X	X	X	
Infusion			X								
Vital signs (pulse, BP, RR, temp)	X	X	X	Prior to infusion and then every 15 min ±5 min after the start of infusion until 2 hrs; continue every hour ±5 min until 4 hrs, then at 6 hrs, and 24 hrs post infusion.						X	
Pulse-Ox			X	Continuously monitor while monitoring for vital signs; record at same time points as for vital signs above.							
Monitor for AE			X	Prior to infusion and then every 15 min ±5 min after the start of infusion until 2 hrs; continue every hour ±5 min until 4 hrs, then at 6 hrs, and 24 hrs post infusion, ±10 mins for all other time points. Daily until discharged or Day 6.			X	X	X	X	X 
12-Lead EKG	X		X 		X						

Evaluation	Initial Screen	Rescreen (if applicable  )	Day 1  Base Line -2 hr pre-infusion	1 hr post infusion ± 15min	6 hr post -1 or +2 hr	Day 2 24 hr post ± 3 hr	If hospitalized			Day 6 (+ 4 days)	Day 30 (+2 days) (by phone)
							Day 3	Day 4	Day 5		
Hematology CBC (if blood products are transfused, then CBC pre and post transfusion)	X	X	X	X	X	X	Minimum is daily CBC			X	
ABO group, Rh type	X										
Coagulation Tests: PT/INR, aPTT, D-dimer, Fibrinogen, TAT, PF 1+2, TEG or ROTEM, TGA	Only PT/INR, aPTT, D-dimer, Fibrinogen	Only PT/INR, aPTT, D-dimer, Fibrinogen	X	X	X	X					

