### ***1.15.4 Instructions for Reconstitution and Administration of Thrombosomes***

See Appendix F – Instructions for Reconstitution and Preparation of Thrombosomes – for instructions for reconstituting the vial(s) of Thrombosomes and preparing Thrombosomes doses for use. Study sites receiving, storing, preparing and administering Thrombosomes should be operating under BSL-2 workplace biosafety measures as applied in the blood establishment setting (AABB Technical Manual, 19th edition, 2017, Chapter 2, Facilities, Work Environment and Safety). Thrombosomes should be kept at room temperature and infused by IV within one hour of reconstitution. Use a Hemo-Nate® filter supplied by the Sponsor, in the administration of the product (see Appendix F – Instructions for Reconstitution and Preparation of Thrombosomes for Administration).

To administer the study material in patients, the investigator may use the central or existing IV line if available. If not, obtain IV access in patient. Begin the administration of normal saline using an infusion administration set with a standard medication injection site. Check the identity

---

 Although preclinical, laboratory, and clinical testing to date do not suggest that Thrombosomes® need to be filtered during administration, the FDA has recommended the use of a blood filter for this study as a precautionary measure. Cellphire conducted studies of several FDA cleared blood filters with pore sizes from 18 to 150 microns. None of the filters tested affected the biologic or physical characteristics of Thrombosomes. The Hemo-Nate® Filter #4020009 (Utah Medical Products, Midvale, UT) has been selected for use in this clinical trial and will be supplied to sites by the sponsor. Selection was based on the material (stainless steel), low priming volume (0.7 ml), 18 micron size, and ease of use.

of the patient with the prepared label. Stop the normal saline infusion and begin administration of the predetermined dose of study material at the rate of 1ml/min through the medication injection site using a syringe infusion device capable of delivery at the required rate. After the infusion, begin administration of the normal saline and use approximately 25 ml to flush the line.

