**Table 6. Requirements Following Patient Withdrawal**

Visit Number	Procedures	Follow-up Required
1 or 1A	Initial screening or Rescreening	None
2 through final visit	Infusion	

• If patient was not infused prior to withdrawing, complete the withdrawal form.

• If infusion was initiated before withdrawal, discontinue the infusion, and complete the final exam and blood draws to assess for safety. Request that patient return for follow-up visits as scheduled to ensure safety. Minimally, obtain patient contact information and perform follow-up phone calls if the patient doesn't come for visits. Provide clinic contact information for procedure-related concerns or patient-initiated follow-up.

• If infusion was completed before withdrawal, complete the final exam and blood draws to assess for safety. Request that patient return for follow-up visits as scheduled to ensure safety. Minimally, obtain patient contact information and perform follow-up phone calls if the patient doesn't come for visits. Provide clinic contact information for procedure-related concerns or patient-initiated follow-up.

Patient interview will be documented by a written record of the interview and patient responses, signed and witnessed by the participant and staff conducting the exit interview at the time of withdrawal.

The anticipated circumstances under which the patient's participation may be terminated by the Investigator are indicated as follows:

- Non-compliance (e.g., no-show for scheduled visit, impairment due to drugs/alcohol, agitation or disruption during visit, inability to follow clinic-established rules concerning conduct)
- Safety issues (e.g., patient does not meet inclusion criteria for ongoing stages of the study, clinic safety due to unacceptable conduct, study cancelled due to product safety)
- Sponsor-initiated study termination
- Investigator-initiated study termination
- IRB of record or FDA study termination

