### **5.2 Safety Population**

The Safety Population will include all patients who were infused with Thrombosomes, regardless of duration of subsequent study participation or adherence to planned follow-up assessments. As patients will be considered enrolled at the start of infusion, the Safety Population will also represent an "enrolled population". The population will be used in descriptive analysis of patient characteristics and disposition, as well as in all safety analyses supporting the Primary Objective and select efficacy analyses supporting the Secondary Objective.

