## 8.6 Infused Thrombosomes

A tabular summary of statistics describing the Thrombosomes infusion doses received by patients will be provided. Specifically, the statistics will describe the following elements:

- Total Volume of Thrombosomes Infused (mL), computed as: ([patient body weight in kg] x [target dose in particles/kg, specific for dose cohort]) ÷ (Thrombosomes lot concentration in particles/mL)
- Interrupted Infusion (Yes/No)
- Reason for Interruption (Adverse Event, Infusion Site or Equipment not Functioning, Patient Declined Infusion, or Other)
- Total Number of Thrombosomes Particles Infused, computed as: (Thrombosomes lot concentration in particles/mL) x (Total Volume of Thrombosomes Infused in mL)
- Total Number of Particles Infused per Kilogram of Patient Body Weight (particles/kg), computed as: (Total Number of Thrombosomes Particles Infused) ÷ (patient body weight in kg)

A data listing will be provided to disclose the elements above for each patient. Note that standard units of calculation and presentation (i.e., particles vs. TGPU and particles/kg vs. TGPU/kg) will be selected prior to database lock. See also Section 3.1, **Table 1**, for more information.

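### SAP 8.6 derives the infused dose from the target dose, so the exposure table reports the full cohort target even for an infusion stopped early

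*SAP*

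**What the plan says.** SAP 8.6 introduces its table as a description of the infusion doses patients received. It then defines three linked quantities:

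- Volume: "Total Volume of Thrombosomes Infused (mL), computed as: ([patient body weight in kg] x [target dose in particles/kg, specific for dose cohort", divided by the lot concentration in particles/mL.
- Total particles: lot concentration times that volume.
- Dose per kg: "Total Number of Particles Infused per Kilogram of Patient Body Weight (particles/kg), computed as: (Total Number of Thrombosomes Particles Infused", divided by body weight.

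The only other elements are a yes/no interruption flag and "Reason for Interruption (Adverse Event, Infusion Site or Equipment not Functioning, Patient Declined Infusion, or Other". The patient listing carries the same elements. The choice between particles and TGPU as units is left open until database lock.

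Partial infusions are foreseen. Protocol Table 6 instructs: "If infusion was initiated before withdrawal, discontinue the infusion, and complete the final exam and blood draws to assess for safety". Such patients stay in the analysis, because under SAP 5.2 "patients will be considered enrolled at the start of infusion" and the Safety Population is everyone infused.

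**The concern.** A table of dose received should contain something that was measured at the infusion. Here all three dose figures come from weight, target and lot concentration, which are known before the infusion begins. The result cannot differ from the plan, whatever happened at the bedside.

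In a dose-escalation study, safety by cohort is read against the dose given, and Protocol 1.9.1 says the data are to support the design of later protocols. A patient whose infusion is stopped for an adverse event is one whose delivered dose matters most. The study report would show that patient at the full target.

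**Working it through.** **Inputs.** Targets T: 9.45 × 10⁷, 1.89 × 10⁸ and 3.78 × 10⁸ particles/kg for Cohorts 1 to 3 (SAP Table 1). Weight W = 70 kg and concentration C = 1.61 × 10⁹ particles/mL (SAP Table 1, footnote 1). Infusion rate from Protocol 1.15.4: "begin administration of the predetermined dose of study material at the rate of 1ml/min through the medication injection site". Adverse event checks from Protocol Table 4: "then every 15 min ±5 min after the start of infusion until 2 hrs". The documents give no fraction delivered, so f below is an assumption shown over a range.

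**1. The plan's own figures.** V = W × T / C. Cohort 1: 70 × 9.45 × 10⁷ / 1.61 × 10⁹ = 4.11 mL. Cohorts 2 and 3 in the same way: 8.22 and 16.43 mL. SAP Table 1 prints 4.1, 8.2 and 16.4 mL, so it is reproduced. The volume formula in SAP 8.6 is this same planning formula.

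**2. The chain in SAP 8.6.**

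- V = W × T / C
- particles = C × V = W × T
- particles/kg = W × T / W = T

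W and C drop out. On 3,000 random combinations of weight and lot concentration, the largest relative deviation from target was 3 × 10⁻¹⁶, which is rounding. The same cancellation occurs in TGPU. Volume in mL and total particles do vary between patients, with weight and lot, but always at the planned amount.

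**3. Partial delivery.** With a delivered volume of f × V, the true dose is f × T.

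| Particles/kg | f = 0.75 | f = 0.50 | f = 0.25 | Reported under SAP 8.6 |
|---|---|---|---|---|
| Cohort 1 | 7.09 × 10⁷ | 4.73 × 10⁷ | 2.36 × 10⁷ | 9.45 × 10⁷ |
| Cohort 2 | 1.42 × 10⁸ | 9.45 × 10⁷ | 4.73 × 10⁷ | 1.89 × 10⁸ |
| Cohort 3 | 2.84 × 10⁸ | 1.89 × 10⁸ | 9.45 × 10⁷ | 3.78 × 10⁸ |

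A Cohort 3 patient stopped halfway has received the Cohort 2 target (8.2 mL) but is reported at 16.4 mL and 3.78 × 10⁸/kg.

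**4. Can a stop fall inside the infusion?** At 1 mL/min the 70 kg infusions last about 4.1, 8.2 and 16.4 minutes. The first scheduled check after the start falls at 10 to 20 minutes, when a Cohort 3 infusion can still be running. A stop at 10 minutes delivers 10 / 16.43 = 60.8% of the dose, or 2.30 × 10⁸/kg. The reported value is 3.78 / 2.30 = 1.64 times the true one.

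**5. Cohort summary, one Cohort 3 patient in 8 at half dose (illustrative).** True mean = (7 × 3.78 × 10⁸ + 1.89 × 10⁸) / 8 = 3.54 × 10⁸, which is 93.75% of target, with SD 6.7 × 10⁷ and minimum 1.89 × 10⁸. The table would show mean, minimum and maximum all equal to 3.78 × 10⁸, with SD 0.

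**The case against.** The strongest reply is that the plan does not hide a failed infusion. The table and listing carry the interruption flag and its reason, including adverse event. SAP 7.2 has a deviation category for non-compliance with study drug administration, and adverse events leading to study discontinuation are listed separately. This stands, so a reader should not infer that the outputs conceal under-delivery altogether. What they lack is the amount given. The flag also does not say whether the infusion was completed, and it would not pick up a volume error without an interruption.

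An interruption is also not the same as a shortened dose. An infusion paused for an equipment fault and then completed delivers the target, and SAP 8.6 reports it correctly. Only a permanent stop is misreported, and the documents give no rate for that.

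The eCRF, which is not among the documents, may record an infused volume. If it does, SAP 8.6 as worded does not use it.

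Finally, the consequence is limited. Summaries are by assigned cohort, no planned test uses received dose, and the DMC outputs listed in SAP Appendix 1 include no exposure table. This also stands, and it bounds the point without removing it.

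**Conclusion.** SAP 8.6 is wrong as written. A table presented as dose received can only return dose planned. Particles/kg equals the cohort target with SD 0 in every cohort, and a Cohort 3 infusion stopped halfway is overstated twofold (3.78 / 1.89). The algebra needs no assumption. The sizes rest on a 70 kg patient, 1.61 × 10⁹ particles/mL, 1 mL/min and an assumed stopping point. If no infusion is stopped early and each planned volume is given, the table will be right, but by assumption and not from data.

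The effect is on reported exposure only. Nothing here implies that patients are overdosed or that escalation decisions rest on a wrong dose.

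A reader might also infer systematic underdosing from the syringe filter, described in Protocol 1.15.4 as having "low priming volume (0.7 ml), 18 micron size, and ease of use". The documents do not support that. A priming volume is not shown to be product lost, no retained volume is stated, and the lot dose table in the EDC (Appendix F.3), which could include an allowance, is not available. No loss is claimed and no change to preparation or administration is proposed.

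**What to change.** In SAP 8.6:

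1. Keep the present formula but call it planned volume.
2. Define volume infused as the recorded administered volume: volume drawn into the syringe minus volume left in it at the end or at stopping.
3. Derive total particles and particles/kg (or the TGPU equivalents) from that volume.
4. Show target dose and percent of target delivered beside these in Table 14.3.8.1 and Listing 16.2.7.1, and keep the interruption flag and reason.
5. Where an infusion was permanently stopped and no volume was recorded, estimate it as running time × 1 mL/min, excluding pauses, capped at the planned volume and labelled as an estimate. If running time is not available either, report the volume as unknown. The exclusion and cap are needed: a completed 16.4 mL infusion with a 5-minute pause would otherwise be estimated at 16.4 + 5 = 21.4 mL.

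The cost is a wording change to one SAP section, one table and one listing, plus two recorded volumes if the eCRF does not already hold them. Target doses and infusion steps do not change. SAP 8.6 already leaves its units to be settled before database lock, so both can be settled together.

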## 6.9 Descriptive Statistics and Notation

Unless stated otherwise, the term "descriptive statistics" refers to frequencies (counts and percentages) for categorical data and the number of patients (or samples), mean, median, standard deviation, interquartile range, minimum, and maximum for continuous data. When fewer statistics are needed for continuous variables and the appropriate (or desired) measure of centrality is the mean, the 95% confidence interval (CI) may be provided as the corresponding measure of dispersion. Likewise, when the appropriate (or desired) measure of centrality is the median, the corresponding dispersion measure to be provided may be the interquartile range or the combination of first and third quartiles, also referred to as 25th and 75th percentiles.

For the presentation of statistical results, standard approaches to determining significant digits will be used. Minimum and maximum values will be presented with the precision of the original values. Means, CIs, medians, interquartile ranges, and quartiles/percentiles will be rounded to 1 decimal place greater than (i.e., to the left of) the precision of the original value. Standard deviations will be rounded to 2 decimal places greater than the precision of the original value.

Percentages will be rounded to the nearest whole number, with values of “<1%” and “>99%” displayed for percentages approaching 0% and 100%, respectively. P-values will be presented with 3 decimal places of precision, and values less than 0.001 will be presented as “<0.001”.

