### **14.3.8 Infused Thrombosomes**

Table 14.3.8.1      Summary of Thrombosomes Infusion Doses – Safety Population

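### SAP 8.6 calculates the infused dose from the target, so the exposure table shows every patient at exactly the cohort target whatever volume was delivered

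*SAP*

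**What the plan says.** SAP 8.6 states that its table describes the doses received. The elements that matter here are these:

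- Volume: "Total Volume of Thrombosomes Infused (mL), computed as: ([patient body weight in kg] x [target dose in particles/kg, specific for dose cohort", divided by the lot concentration in particles/mL.
- Total particles: "Thrombosomes lot concentration in particles/mL) x (Total Volume of Thrombosomes Infused in mL".
- Particles/kg: total particles divided by body weight.
- Interruption: a Yes/No item, plus "Reason for Interruption (Adverse Event, Infusion Site or Equipment not Functioning, Patient Declined Infusion, or Other".

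The same elements go into a patient-level listing. In SAP Appendix 2 the outputs are Table 14.3.8.1, "Summary of Thrombosomes Infusion Doses", and Listing 16.2.7.1. SAP 6.9 sets the statistics for such a table: number of patients, then "mean, median, standard deviation, interquartile range, minimum, and maximum for continuous data".

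Infusions that stop part-way are foreseen. Protocol Table 6 says "If infusion was initiated before withdrawal, discontinue the infusion", and SAP 8.6 lists an adverse event first among its reasons for interruption. Under SAP 5.2, "patients will be considered enrolled at the start of infusion", so a partly infused patient belongs to the Safety Population on which these outputs are based.

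**The concern.** The formula for volume infused in SAP 8.6 is the one used in footnote 1 of SAP Table 1 to plan a dose. No delivered quantity enters any of the three dose formulas, and the interruption item enters none of them. The dose columns therefore restate the plan.

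The primary objective is safety across three escalating doses, with 8 patients per cohort. If one patient receives part of a dose, a reader relating that patient's events to exposure needs to know how much was given. Table 14.3.8.1 and Listing 16.2.7.1 are the planned outputs for dose received, and as defined they cannot supply that figure.

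**Working it through.** **Inputs.** Cohort targets D = 9.45 x 10^7, 1.89 x 10^8 and 3.78 x 10^8 particles/kg (SAP Table 1). Reference weight W = 70 kg and mean lot concentration C = 1.61 x 10^9 particles/mL (SAP Table 1, footnote 1). Infusion rate 1 ml/min (protocol 1.15.4). The fraction delivered, f, is assumed; the documents give no interruption rate.

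**Step 1: reproduce the plan's volumes.** V = W x D / C.

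- Cohort 1: 70 x 9.45 x 10^7 / 1.61 x 10^9 = 4.109 mL (stated 4.1).
- Cohort 2: 70 x 1.89 x 10^8 / 1.61 x 10^9 = 8.217 mL (stated 8.2).
- Cohort 3: 70 x 3.78 x 10^8 / 1.61 x 10^9 = 16.435 mL (stated 16.4).

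All three agree, so the planning formula itself is sound.

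**Step 2: follow SAP 8.6 through to particles/kg.**

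- Total particles: P = C x V = C x (W x D / C) = W x D.
- Particles/kg: P / W = D.

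The result is the target, exactly. A numerical check over 3 targets, 5 weights (45 to 130 kg) and 4 concentrations (1.2 x 10^9 to 2.1 x 10^9, an assumed range), 60 combinations in all, gave a maximum relative deviation from target of 0. Under SAP 6.9 the particles/kg row must therefore print mean = median = minimum = maximum = target, with SD 0, in each cohort.

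**Step 3: compare with what a partial infusion delivers.** With the delivered volume f x V, the true value is C x f x V / W = f x D. For a 70 kg Cohort 3 patient:

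| f | Delivered volume (mL) | True particles/kg | SAP 8.6 reports | Reported / true |
|---|---|---|---|---|
| 1.00 | 16.4 | 3.78 x 10^8 | 3.78 x 10^8 | 1 |
| 0.75 | 12.3 | 2.835 x 10^8 | 3.78 x 10^8 | 1.33 |
| 0.50 | 8.2 | 1.89 x 10^8 (Cohort 2 target) | 3.78 x 10^8 | 2 |
| 0.25 | 4.1 | 9.45 x 10^7 (Cohort 1 target) | 3.78 x 10^8 | 4 |

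At 1 ml/min the full infusion takes about 16.4 minutes, so these rows correspond to stopping at about 12.3, 8.2 and 4.1 minutes. The first row also covers an infusion that was paused and then completed: it is flagged as interrupted and its dose is reported correctly.

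**Step 4: effect on the cohort row.** Suppose one of 8 Cohort 3 patients stops at f = 0.50 and the other seven receive the full dose.

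- True mean: (7 x 3.78 x 10^8 + 1.89 x 10^8) / 8 = 3.54 x 10^8.
- True sample SD: 6.7 x 10^7. True minimum: 1.89 x 10^8.
- SAP 8.6 prints mean 3.78 x 10^8, SD 0, minimum 3.78 x 10^8.

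**The case against.** The strongest reply is that the consequence is small. Each patient has one short infusion, about 4 to 16 minutes at 70 kg. The documents give no reason to expect many incomplete infusions, and if every planned volume is given in full the table is right. No test, analysis population, stopping rule or escalation step uses these outputs, and the tables listed for the DMC in SAP Appendix 1 do not include exposure. All of this stands, and it limits the point to descriptive exposure reporting.

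The SAP also has other signals. The listing shows the interruption and its reason for each patient, and SAP 7.2 has a deviation category for non-compliance in administering the study drug, with its own listing. These narrow the gap without closing it, because none of them gives the amount delivered. The Yes/No item also cannot separate a completed infusion from an abandoned one.

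Four stronger readings are tempting, and the documents do not support them:

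- **That the delivered volume is not recorded.** The case report forms are not among the documents, and the SAP introduction refers to them for data collection. What can be said is that SAP 8.6 does not use a recorded volume.
- **That an adverse event which stopped an infusion would be taken as occurring at the full dose.** The listing shows the interruption and its reason beside the dose. The adverse event tables are by cohort, so the patient would stay in the same column even with a corrected exposure figure.
- **That every interrupted infusion is misreported.** Only those where the delivered volume differs from plan are.
- **That leaving the unit open is a further fault.** SAP 8.6 says that "standard units of calculation and presentation (i.e., particles vs. TGPU and particles/kg vs. TGPU/kg) will be selected prior to database lock". At the SAP's own mean concentrations the Cohort 3 volume is 16.43 mL by particles and 70 x 660 / 2,800 = 16.50 mL by TGPU, a gap of 0.4%. Choosing a unit of presentation before lock is ordinary practice, and the choice cannot alter the volume once a recorded one is used.

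**Conclusion.** The point holds as an error in the stated rule. The section says it reports dose received, and its formulas return the target for every patient by algebra, with no assumption beyond using the same weight and lot concentration throughout, as the SAP states. Rounding of the volume would add only trivial scatter.

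Where the delivered volume is a fraction f of plan, the reported dose is too high by a factor of 1/f: 1.33, 2 or 4 in the assumed examples. Whether any such patient occurs is unknown. Because the plan itself provides for interrupted and discontinued infusions and keeps those patients in the Safety Population, the change is worth making. It does not bear on cohort order, the planned tests or the DMC's listed tables.

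**What to change.** In SAP 8.6, define Total Volume Infused as the volume actually infused, as recorded for each patient. Derive total particles as the lot concentration times that volume, and particles/kg as that total over weight. Keep the present formula under the name planned volume. Show planned volume, actual volume and percent of target (100 x actual / planned) in Table 14.3.8.1 and Listing 16.2.7.1, beside the interruption flag and reason. A paused and completed infusion would then show 100%, and one stopped halfway 50%.

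The cost is one redefined volume, from which the other two quantities follow, and a few extra columns. The small downside is that the delivered volume must be captured if the case report form does not already do so.
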